3.1. Study Rationale

Lasmiditan is a small molecule serotonin (5- hydroxytryptamine_{1F}) receptor agonist being developed for the acute treatment of migraine.

Topiramate taken daily is indicated for prophylaxis of migraine and may be used concomitantly with lasmiditan in the intended patient population. As such, it is important to understand potential interactions between drugs commonly used in treating migraine, specifically, whether co-administration of such agents results in an increased safety risk or any change in the exposure to either (or both). Very common adverse events (AEs) ($\geq 1/10$) associated with topiramate include dizziness, somnolence, paresthesia, nausea, and fatigue (Topiramate US Prescribing Information [<https://www.topamax.com/files/topamax.pdf>]). Given the occurrence of similar AEs observed following administration of single doses of lasmiditan as documented in Section 3.2, it is important to understand the tolerability when both are co-administered.

Topiramate is not extensively metabolized and is primarily eliminated unchanged in the urine. Six metabolites have been identified in humans, none of which constitutes more than 5% of an administered dose. The metabolites are formed via hydroxylation, hydrolysis, and glucuronidation. In vitro studies indicate that topiramate does not inhibit enzyme activity for cytochrome P450 (CYP1A2, CYP2A6, CYP2B6, CYP2C9, CYP2D6, CYP2E1, and CYP3A4/5 isozymes. In vitro studies indicate that topiramate is a mild inhibitor of CYP2C19 and a mild inducer of CYP3A4 (Topiramate US Prescribing Information [<https://www.topamax.com/files/topamax.pdf>]).

Following exploratory analysis of human plasma samples from adult subjects receiving oral lasmiditan, 3 major human metabolites (M7, M8, and [S,R]-M18) were observed. Ketone reduction of lasmiditan to M8 (alcohol) appears to be the major metabolic pathway, presumably via non-CYP enzymes. In human liver microsomes, CYP1A2 and CYP3A4 appear to be involved to a minor extent in lasmiditan metabolism. Unchanged lasmiditan comprises approximately 2% of the dose excreted in urine. Lasmiditan is a very weak inhibitor of CYP3A4, CYP2D6, and P-glycoprotein.

Although the probability of a pharmacokinetic (PK) drug-drug interaction between lasmiditan and topiramate is considered very low based on the low inhibitory potential of both drugs and their diverse elimination pathways, a study of their PK interaction is being conducted as a secondary endpoint to the safety and tolerability of both drugs because of the likelihood for concomitant use in clinical practice.

3.2. Background

Across the completed Phase 1, 2, and 3 clinical studies, doses of 0.1 to 400 mg of lasmiditan were evaluated in healthy subjects or patients with migraine. To date, lasmiditan has been administered to 230 healthy subjects and to 1632 patients with migraine. Compared with placebo, the most frequently reported lasmiditan treatment-emergent adverse events (TEAEs) included dizziness, paresthesia, somnolence, fatigue, lethargy, and nausea. The majority of these

TEAEs were mild or moderate in severity and none led to subject withdrawal. One patient experienced a serious adverse event (SAE) of dizziness that was moderate in severity (lasmiditan 200 mg).

Oral tablet doses of lasmiditan up to 400 mg did not result in any clinically relevant changes in electrocardiograms (ECGs) (including QT interval/corrected QT interval [QTc]) following administration to healthy subjects. In the thorough QT study in healthy subjects, no clinically significant changes in blood pressure, heart rate, or 12-lead ECG were observed at the 100- or 400-mg single-dose levels. Lasmiditan caused no significant QT prolongation at either dose.

In healthy subjects, peak plasma concentrations of lasmiditan were observed approximately 1 to 2.5 hours after a single oral dose ranging from 25 to 400 mg, and the geometric mean terminal half-life was approximately 4 to 6 hours. Lasmiditan exhibited dose-linear PK; low to moderate intersubject variability in exposure was observed across doses (% coefficient of variation up to 61% and 45% for maximum observed drug concentration [C_{max}] and area under the concentration versus time curve [AUC], respectively). Co-administration of lasmiditan with a high-fat diet led to a delay in median time of maximum observed drug concentration (t_{max}) value by approximately 1 hour and a modest (~20%) increase in lasmiditan C_{max} and AUC values, relative to that under fasted conditions.

3.3. Benefit/Risk Assessment

The primary objective of this study is to evaluate the safety and tolerability of a single dose of lasmiditan in combination with topiramate in healthy subjects. There is no anticipated therapeutic benefit for the subjects.

No clinically significant safety or tolerability concerns have been identified in subjects to date for lasmiditan up to the highest single oral dose given (400 mg). Dosing of lasmiditan in this study will be conducted in an inpatient setting, and subjects will be monitored in the clinical research unit (CRU) for at least 48 hours after dosing.

More information about the known and expected benefits, risks, SAEs, and reasonably anticipated AEs of lasmiditan is to be found in the Investigator's Brochure (IB).

Topiramate is a marketed drug and will be administered within a dose titration regimen that has been tolerated in previous PK studies in healthy subjects (e.g. Bialer et al. 2013; Manitpisitkul et al. 2014a,b).

More detailed information about the known and expected benefits and risks of topiramate may be found in the following: 2017 US Prescribing Information.

4. Objectives and Endpoints

Table LAHT.1 shows the objectives and endpoints of the study.

Table LAHT.1. Objectives and Endpoints

Objectives	Endpoints
Primary To evaluate the safety and tolerability of a single dose of lasmiditan in combination with topiramate in healthy subjects.	A summary of the number of treatment-emergent adverse events and serious adverse events
Secondary To evaluate the pharmacokinetics of lasmiditan alone and in combination with topiramate in healthy subjects.	C_{max} , t_{max} , $AUC(0-t_{last})$ and $AUC(0-\infty)$
To evaluate the pharmacokinetics of topiramate alone and in combination with lasmiditan.	C_{max} , t_{max} , and AUC_{τ}
Exploratory To evaluate the pharmacokinetics of lasmiditan metabolites alone and in combination with topiramate in healthy subjects.	C_{max} , t_{max} , $AUC(0-t_{last})$, and $AUC(0-\infty)$

Abbreviations: $AUC(0-t_{last})$ = area under the concentration versus time curve from time zero to time t , where t is the last time point with a measurable concentration; $AUC(0-\infty)$ = area under the concentration versus time curve from zero to infinity; AUC_{τ} = area under the concentration versus time curve during 1 dosing interval; C_{max} = maximum observed drug concentration; t_{max} = time to C_{max} .

5. Study Design

5.1. Overall Design

This is a Phase 1, parallel, placebo-controlled, fixed-sequence study with open-label administration of topiramate and investigator- and subject-blind administration of lasmiditan/placebo conducted in healthy subjects.

Subjects will be admitted to the CRU on Day -1 and are expected to remain a resident until all assessments are completed on Day 16; however, subjects may be allowed to leave the CRU at the discretion of the investigator.

[figure not shown]
Study governance considerations are described in detail in [Appendix 3](#).

Lasmiditan and topiramate doses will be administered at the CRU. Subjects will be randomly assigned in a 2:1 ratio to receive lasmiditan or placebo on both lasmiditan dosing days (Days 1 and 14). A single oral dose of study drug (200-mg lasmiditan or placebo) will be administered in the morning on Day 1. After lasmiditan wash-out, topiramate will be titrated up to 100 mg on Days 3 to 13. On Day 14, 1 oral dose of lasmiditan 200 mg or placebo will be co-administered with the final topiramate dose (50 mg) in the morning.

Blood sampling for PK assessment will be conducted predose and at time points up to 48 hours postdose on Days 1 and 14 for the measurement of plasma concentrations of lasmiditan and its metabolites. Blood samples will also be collected predose and up to 12 hours postdose on Days 13 and 14 for the measurement of plasma concentrations of topiramate.

A follow-up visit will take place at least 10 days following co-administration of lasmiditan and topiramate (Day 14).

[Figure LAHT.1](#) illustrates the study design.

Abbreviations: LY = lasmiditan (200 mg); n = number of subjects in each group; P = placebo.

Symbols: “25” inside a circle = one 25-mg tablet of topiramate; gray pentagon = lasmiditan dose or placebo.

Figure LAHT.1. Illustration of study design for Protocol H8H-MC-LAHT.

5.2. Number of Participants

Approximately 30 subjects may be enrolled so that at least 21 subjects complete the study. For purposes of this study, a subject completes the study when all scheduled procedures shown in the Schedule of Activities have been finished.

5.3. End of Study Definition

End of the study is the date of the last visit or last scheduled procedure shown in the Schedule of Activities (Section 2) for the last subject.

5.4. Scientific Rationale for Study Design

Subjects will be randomly assigned to 1 of 2 treatment arms. Treatment arms run in parallel and both receive the same topiramate dosing schedule. One treatment arm will receive lasmiditan (200 mg) on Days 1 and 14 when the other receives a lasmiditan placebo to control for observed AEs.

The study has a double-blind (subject- and investigator-blind), fixed-sequence design in which each subject receives lasmiditan or placebo alone, topiramate alone, and lasmiditan or placebo co-administered with topiramate, allowing each subject to act as his/her own control for safety and PK comparisons. A single 200-mg dose of lasmiditan was selected as it is the highest

potential recommended dose for lasmiditan. The washout period between lasmiditan doses of 14 days is considered sufficient based on the half-life of lasmiditan of approximately 4 to 6 hours. Topiramate will be administered using a titration schedule over a period of 12 days to aid tolerability, with a single dose of lasmiditan or placebo co-administered on the final day, to ensure that topiramate concentrations are at steady state at the time of lasmiditan or placebo dosing.

5.5. Justification for Dose

The dose level of 200-mg lasmiditan has been well tolerated in previous studies of healthy subjects; 200 mg is expected to be the highest recommended single dose of lasmiditan.

As described in the label, topiramate is initiated at 25 mg/day (Day 3), increased to 50 mg/day (Days 4 to 7), and maintained at 100 mg/day (Days 8 to 13). The recommended dosage for migraine prophylaxis is 100 mg/day (Topiramate US Prescribing Information [<https://www.topamax.com/files/topamax.pdf>]). Similar topiramate titration schedules to reach steady state in healthy subjects demonstrate acceptable safety profiles (Bialer et al. 2013; Manitpisitkul et al. 2014a) and are generally well tolerated (Manitpisitkul et al. 2014b).

6. Study Population

Eligibility of subjects for the study will be based on the results of screening medical history, physical examination, vital signs, clinical laboratory tests, and ECG.

The nature of any conditions present at the time of the physical examination and any preexisting conditions will be documented.

Screening may occur up to 28 days prior to enrollment. Subjects who are not enrolled within 28 days of screening may be subjected to an additional medical assessment and/or clinical measurements to confirm their eligibility.

Prospective approval of protocol deviations to recruitment and enrollment criteria, also known as protocol waivers or exemptions, is not permitted.

6.1. Inclusion Criteria

Subjects are eligible for inclusion in the study only if they meet all of the following criteria at screening:

- [1] are overtly healthy males or females, as determined by medical history and physical examination.
 - [1a] male subjects:
are not required to adhere to contraceptive requirements.
 - [1b] female subjects:
of non-childbearing potential, i.e., postmenopausal or permanently sterile following hysterectomy, bilateral salpingectomy, or confirmed tubal occlusion (not tubal ligation), as determined by written or spoken medical history. Postmenopausal is defined as spontaneous amenorrhea for at least 12 months, and a plasma follicle-stimulating hormone level greater than 40 mIU/mL, unless the subject is taking hormone replacement therapy (HRT).
- [2] are aged 18 to 65 years at the time of screening.
- [3] have a body mass index (BMI) of 19.0 to 35.0 kg/m², inclusive, at the time of screening.
- [4] have clinical laboratory test results within normal reference range for the population or investigative site, or results with acceptable deviations that are judged to be not clinically significant by the investigator.
- [5] have venous access sufficient to allow for blood sampling as per the protocol.
- [6] are reliable and willing to make themselves available for the duration of the study and are willing to follow study procedures.
- [7] have given written informed consent approved by Lilly and the ethical review board (ERB) governing the site.

6.2. Exclusion Criteria

Subjects will be excluded from study enrollment if they meet any of the following criteria at screening and/or enrollment:

- [8] are CRU personnel directly affiliated with this study and their immediate families. Immediate family is defined as a spouse, biological or legal guardian, child, or sibling.
- [9] are Lilly or Covance employees.
- [10] are currently enrolled in a clinical study involving an investigational product (IP) or any other type of medical research judged not to be scientifically or medically compatible with this study.
- [11] have known allergies to lasmiditan, topiramate, related compounds or any components of the formulation of lasmiditan or topiramate.
- [12] are persons who have previously received the IP in this study, withdrawn from this study, or received lasmiditan in any other study investigating lasmiditan.
- [13] have participated (dosed with IP [lasmiditan or placebo]), within the past 30 days, in a clinical study involving an IP. If the previous IP has a long half-life, 5 half-lives or 30 days (whichever is longer) should have passed.
- [14] have a history of, or ECG findings of, clinically significant bradycardia, heart block, tachy or brady arrhythmias, or have any other abnormality in the 12-lead ECG that, in the opinion of the investigator, increases the risks associated with participating in the study.
- [15] have an abnormal supine blood pressure, defined as systolic blood pressure <90 or >140 mmHg or diastolic blood pressure <60 or >90 mmHg at screening. Repeat assessments may be performed to confirm eligibility.
- [16] have a significant history of or current cardiovascular, respiratory (including bronchospasm or bronchial asthma, or chronic obstructive airways disease), hepatic, renal, gastrointestinal, endocrine, hematological, or neurological disorders capable of significantly altering the absorption, metabolism, or elimination of drugs; of constituting a risk when taking the study medication; or of interfering with the interpretation of data. Appendectomy, splenectomy, and cholecystectomy are considered as acceptable.
- [17] show a history of central nervous system (CNS) conditions such as strokes, transient ischemic attacks, significant head trauma, CNS infections, migraines, brain surgery, or any other neurological conditions that, in the opinion of the investigator, increases the risk of participating in the study.
- [18] have known or ongoing psychiatric disorders considered clinically significant by the investigator or demonstrate suicidal ideation on the Columbia Suicide Severity Rating Scale (C-SSRS).

- [19] currently use, or within the past 1 year used recreational drugs, or showed evidence of substance dependence within the past 6 months based on history at screening visit.
- [20] show evidence of human immunodeficiency virus (HIV) infection and/or positive human HIV antibodies.
- [21] show evidence of hepatitis C and/or positive hepatitis C antibody.
- [22] show evidence of hepatitis B and/or positive hepatitis B surface antigen.
- [23] are women with a positive pregnancy test or women who are lactating.
- [24] intend to use over-the-counter or prescription medication, dietary supplements within 14 days prior to dosing and until study discharge (apart from occasional acetaminophen or HRT).
- [25] have donated blood of more than 500 mL within 1 month prior to the screening visit.
- [26] have an average weekly alcohol intake that exceeds 21 units per week (males up to the age of 65 years) and 14 units per week (females), or are unwilling to stop alcohol consumption 48 hours prior to dosing until the completion of the study (1 unit = 12 oz or 360 mL of beer; 5 oz or 150 mL of wine; 1.5 oz or 45 mL of distilled spirits).
- [27] have a clinically significant abnormality in the neurological examination.
- [28] have current or a history of orthostatic hypotension (>20-mmHg drop in systolic blood pressure, or >10-mmHg drop in diastolic blood pressure) with or without dizziness and/or syncope at screening or admission to the CRU upon repeat testing.
- [29] are unwilling to refrain from tobacco- or nicotine-containing products while in the CRU or are unable to abide by CRU restrictions.
- [30] have an estimated glomerular filtration rate using Modification of Diet in Renal Disease <60 mL/min/1.73 m².
- [31] have a history of glaucoma.
- [32] have a history of galactose intolerance, Lapp lactase deficiency, or glucose-galactose malabsorption.
- [33] in the opinion of the investigator or sponsor, are unsuitable for inclusion in the study.

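### Exclusion [13] limits the 30-day washout trigger to prior lasmiditan or placebo, so a different recent investigational product without a long half-life has no clearly stated washout

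*Protocol*

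**What the plan says.** Protocol section 6.2 deals with earlier trial exposure in two criteria.

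- **[12]** excludes anyone who has already had this study's IP, has withdrawn from this study, "or received lasmiditan in any other study investigating lasmiditan". It has no time limit.
- **[13], first sentence,** excludes those who "have participated (dosed with IP [lasmiditan or placebo]), within the past 30 days, in a clinical study involving an IP".
- **[13], second sentence,** adds: "If the previous IP has a long half-life, 5 half-lives or 30 days (whichever is longer) should have passed". It carries no bracket.

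Three other criteria come near the subject. [10] excludes those who "are currently enrolled in a clinical study involving an investigational product (IP"), or who are in other incompatible research. [24] excludes those who "intend to use over-the-counter or prescription medication, dietary supplements within 14 days prior to dosing and until study discharge", with exceptions for occasional acetaminophen and hormone replacement. [33] excludes those who, "in the opinion of the investigator or sponsor, are unsuitable for inclusion in the study".

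Appendix 1 defines an IP generally, as an active ingredient or placebo under test or used as a reference in a clinical study. Section 6.2.1 says that [10] to [33] mainly serve to remove conditions and medication use that could confound the endpoints. Section 6 does not permit waivers of the entry criteria.

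**The concern.** A washout rule for recent trial participants should keep out people who may still carry another study's drug or its effects. The bracket in [13] attaches the 30-day bar to the two exposures for which it does least: lasmiditan, which [12] already bars permanently, and placebo. It leaves out the exposure for which a washout matters, a different investigational drug.

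The subjects are healthy volunteers for whom section 3.3 anticipates no therapeutic benefit. Giving them lasmiditan and topiramate soon after another investigational product is first a matter of subject protection.

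It is also an avoidable confounder. The lasmiditan comparison has a fixed order, with Day 1 always the reference and Day 14 always the test. The model in SAP section 9.3.2 has a treatment effect and a random subject effect, so treatment and day cannot be separated. A prior drug acting more on Day 1 than on Day 14 would be read as an effect of topiramate.

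**Working it through.** **Step 1. What the literal text of [13] adds.**

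| Recent exposure in another study | Reached by [13], first sentence? | Reached elsewhere? |
|---|---|---|
| Lasmiditan | Yes | Yes, [12], without time limit |
| Placebo | Yes | Not needed; no active drug |
| Different IP, long half-life | No | [13], second sentence, if read on its own |
| Different IP, half-life not long | No | Not clearly |

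For the last row, [10] applies only while the person is still enrolled in the other study. [24] names over-the-counter and prescription medication and supplements, not investigational drugs. [33] permits exclusion but does not require it.

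**Step 2. Whether the second sentence can be about lasmiditan.** Protocol section 3.2 says that "the geometric mean terminal half-life was approximately 4 to 6 hours". Five half-lives are 5 × 4 = 20 h to 5 × 6 = 30 h, against 30 days = 30 × 24 = 720 h. The five-half-life limb can never bind for lasmiditan and means nothing for placebo, so the sentence must have other drugs in view and the bracket contradicts it.

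**Step 3. Where the undefined term leaves a gap.** Five half-lives exceed 30 days only when the half-life exceeds 30 / 5 = 6 days. If a site took that as the meaning of long, a different drug with a half-life of up to 6 days would have no stated washout. A lower threshold would make the gap smaller. The protocol gives none.

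**Step 4. Which drugs could act unequally on Days 1 and 14.** The fraction left is 0.5^(elapsed time / half-life). Assume the last prior dose was 7 days before Day 1: 168 h have elapsed at Day 1, and 168 + 13 × 24 = 480 h at Day 14. The half-lives are assumed.

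| Prior drug's half-life | Left on Day 1 | Left on Day 14 |
|---|---|---|
| 6 h | about 0% | about 0% |
| 24 h | 0.8% | about 0% |
| 72 h | 19.8% | 1.0% |
| 168 h | 50% | 13.8% |

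Residual drug matters only when the half-life is of the order of days.

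**Step 5. Illustrative shift in the lasmiditan ratio.** The plan gives no figure to reproduce; protocol section 10.1 states that the study is not powered for hypothesis testing. With 2:1 allocation, the lasmiditan arm has 30 × 2/3 = 20 subjects if all complete, or 21 × 2/3 = 14 at the minimum number of completers if the ratio is kept. If k of n subjects have Day 1 exposure multiplied by f, and the effect is gone by Day 14, the Day 14 to Day 1 geometric mean ratio is multiplied by f^(−k/n). For k = 1:

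- f = 1.25: 1.25^(−1/20) = 0.989 (−1.1%); 1.25^(−1/14) = 0.984 (−1.6%).
- f = 2: 2^(−1/20) = 0.966 (−3.4%); 2^(−1/14) = 0.952 (−4.8%).

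A Day 1 reduction by the same factors moves the ratio up by 1.1% to 5.1%. The documents supply no value for f or k.

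**The case against.** The strongest reply is that the second sentence of [13] has no bracket, speaks of an earlier IP in general, and so already covers long-half-life drugs. By Step 4 these are the main source of residual drug on Day 1. [10] will catch some people dosed only days before, because they are still enrolled elsewhere, and [33] lets the investigator or sponsor refuse others. A sensible site may apply the intended meaning. All of this stands, and it narrows the gap. It does not close it: the long-half-life condition is undefined, [33] is optional, and a person who has left the other study falls outside [10].

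A reader might infer that anyone dosed with any other investigational drug is eligible and will bias the Day 14 versus Day 1 comparison. The documents do not support that. The second sentence can be read to exclude part of that group. Protocol section 3.1 describes lasmiditan as cleared mainly by ketone reduction, presumed not to involve CYP enzymes, with CYP1A2 and CYP3A4 playing a minor part, so a twofold change is an assumption. Enzyme induction can outlast the drug that caused it, but nothing in the documents makes that likely here. The comparison is a secondary objective with no stated no-effect bounds, so no planned decision is shown to change.

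A reader might also infer that a prior drug's adverse effects would simply enter the Day 1 treatment-emergent count. Under SAP section 9.4.1, an event already present before dosing counts only if it worsens afterwards. The concurrent randomised placebo arm (protocol section 5.4) means such events would not systematically favour one arm. They could still add noise in arms of this size.

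**Conclusion.** The point holds as an error in an operative eligibility rule. The bracket in [13] conflicts with the criterion's own second sentence, largely duplicates [12], and departs from the general definition of IP in Appendix 1. Applied as written, the criteria state no clear washout for a person who has left another study and was recently dosed with a different product whose half-life is not long.

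The consequence is mainly one of subject protection and avoidable confounding. PK bias is possible but not shown. It would be about 1% to 5% in the lasmiditan ratio per affected subject, assuming 14 to 20 paired subjects, a 1.25- to 2-fold change in Day 1 exposure, and no remaining effect on Day 14. How many such volunteers would present cannot be judged from the documents.

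**What to change.** Reconcile [13] with its second sentence, with [12] and with Appendix 1. Either delete the bracket or generalise it, so that the criterion excludes people dosed with any IP, active or placebo, in another clinical study within the past 30 days. Keep the second sentence and its interval unchanged. Once the 30 days apply to every IP, the second sentence extends the wait only when the half-life exceeds 6 days (30 / 5), so the undefined term ceases to matter in practice.

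This is a one-line protocol amendment. It introduces no new interval and needs no change to the SAP. The cost is that a few volunteers recently in other trials become ineligible.
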